### **Outcome Measure(s)**

The primary outcome will be the within-individual absolute difference in systolic blood pressure from baseline to the first blood pressure after the ECT stimulus.

Secondary outcomes include the within-individual differences of heart rate at 15 and 30 seconds post stimulus, absolute difference in diastolic blood pressure from baseline to the first blood pressure after the ECT stimulus, maximum and minimum heart rates, unit doses of nitroglycerin, esmolol, phenylephrine, ephedrine, EEG and motor seizure duration, use of lidocaine, atropine or epinephrine, total in-room time, time to return of spontaneous ventilation after induction, severity of headache in the post anesthesia care unit, and satisfaction with the anesthetic post-procedure.

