## **Effects of Premedication with Alfentanil on Hemodynamics During and Immediately Following Electroconvulsive Therapy**

**Principal Investigator: [name]**

### **Background**

Electroconvulsive therapy (ECT) is a mainstay of treatment for patients with medication refractory mood disorders. The success of the therapy rests on achieving an adequate generalized tonic/clonic seizure. Multiple ECTS are usually required to achieve the desired effect. For the safety and well-being of the patient, a short general anesthetic is utilized during the ECT.

Electroconvulsive therapy is associated with brief, often dramatic hemodynamic alterations that are dangerous to the patient. This cardiovascular response is caused by activation of the autonomic nervous system and consists of an initial parasympathetic response rapidly followed by sympathetically mediated tachycardia and hypertension. The sympathetic response results in increased myocardial oxygen demand and ECT treatment has been associated with postprocedure increases in cardiac troponin, raising concern for clinically significant myocardial injury (Duma A, et al). The ultra-short acting synthetic opioid alfentanil has a rapid onset and duration of action that mirrors the duration of hemodynamic perturbation associated with ECT while having minimal or no effect on the duration or quality of the seizure. This drug may be effective in blunting the hemodynamic perturbations associated with ECT with minimal side effects.

Alfentanil is a FDA approved narcotic utilized to blunt the hemodynamic response to stimulating portions of a procedure at the discretion of the anesthesia provider in the conduct of general anesthesia. The effect of alfentanil on patient hemodynamics immediately following ECT has been studied only once on a small number of patients (n=21) receiving etomidate anesthesia and never on patients receiving methohexitol anesthesia (van den Broek, et al). Induction with methohexitol as opposed to etomidate is the preferred anesthetic agent as it reduces the seizure threshold in usual induction doses. We propose a double-blind, placebo-controlled study on patients receiving ECT with methohexitol anesthesia that investigates the effects of alfentanil given post-induction of general anesthesia but pre-treatment with ECT on the post-procedure hemodynamics.

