### **Methods and Measures**

A prospective, randomized, double blind, placebo-controlled AB/BA crossover study is planned in patients electively scheduled to undergo electroconvulsive therapy to treat their medication refractory mood disorders. We aim to have 200 evaluable treatments involving the consent of an estimated 100 subjects. As patients normally require more than 1 electroconvulsive therapy to treat their condition, the patient's consent will allow them to participate in this research study in each of two treatments.

Patients will undergo induction of general anesthesia with methohexitol 1 mg/kg and succinylcholine 1 mg/kg in a standardized anesthetic protocol that is nearly identical to the usual institutional standard of care for electroconvulsive therapy. A copy of the anesthetic protocol is posted for the providers reference at the point of care. Members of the study team will be responsible for randomization of the patients and preparation of the blinded study medication. Randomization to either placebo first then alfentanil or the converse will be carried out on the morning of the first study treatment and allocation concealed within a computerized randomization and data collection instrument (REDCap). Calculation of the study dose is done per the FDA package insert using an automated system within REDCap. Alfentanil (20 mcg/kg) diluted with normal saline to 10cc or placebo, consisting of 10 cc normal saline will be obtained from the OR pharmacy and placed in an identical 10 cc syringe labeled with the patient's name and "Study Drug". Any unused quantity of alfentanil will be wasted per hospital policy in the OR pharmacy. The study drug will be administered by the blinded anesthesia provider caring for the patient per the anesthetic protocol. Data will be collected by members of the study team who are blinded to the randomization. Data will be collected and secured in REDCap stored on the institution's secure internal servers.

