### **INDUCTION**

Standard induction for ECT with methohexitol 1 mg/kg and succinylcholine 1 mg/kg

After establishment of an adequate mask airway, and confirmation of adequate impedance on the ECT machine, the study medication (alfentanil or placebo) IV will be administered. A timer on the anesthesia monitor will be started.

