### **60 SECONDS AFTER STUDY DRUG ADMINISTRATION**

ECT stimulus applied

During the procedure in the operating room, blood pressure and heart rate will be monitored as per standard of care (blood pressure every 1 minute and continuous electrocardiogram, pulse oximetry, and capnography while in the procedure room) until the patient is spontaneously ventilating adequately per anesthesia discretion. Hypertension will be treated if the systolic blood pressure exceeds 185 mmHg using nitroglycerin 400 mcg/mL per usual institutional practice. The full range of usual antiarrhythmic, vasopressor and antihypertensive medications including lidocaine, esmolol, phenylephrine, epinephrine, atropine and ephedrine will be available for use by the anesthesia team should they be required. Use of these medications will be tracked and recorded by the study team. After restoration of adequate spontaneous ventilation the patient will then be moved to recovery for subsequent discharge. Evaluation will be done by study personnel to assess the presence of headache or other potential adverse events prior to discharge, and patient satisfaction with the anesthetic.

Prior to discharge the subjects will be asked to rate the severity of headache (if present) as well as the satisfaction with the anesthetic received. Both will be rated on a scale of 0=no headache as all up to 10=worst headache ever, as well as 0=not satisfied with anesthetic at all up to 10=most definitely satisfied with the anesthetic received.

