### **Analytical Plan**

Results will be analyzed initially using a paired T Test for continuous variables and a Wilcoxon signed-rank test for ordinal variables.

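### The primary blood pressure reading has no set time after the stimulus, so a patient's two sessions can be read at different points of a fast response, at a cost in precision

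*Combined protocol and SAP*

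**What the plan says.** The Outcome Measure(s) section defines the primary outcome as the "within-individual absolute difference in systolic blood pressure from baseline to the first blood pressure after the ECT stimulus". One secondary outcome follows the same rule: "absolute difference in diastolic blood pressure from baseline to the first blood pressure after the ECT stimulus". Heart rate is treated differently, with fixed times: "heart rate at 15 and 30 seconds post stimulus".

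The section on the period from 60 seconds after study drug sets procedure-room monitoring as "blood pressure every 1 minute and continuous electrocardiogram, pulse oximetry, and capnography while in the procedure room". Under INDUCTION, when the study drug is given, "A timer on the anesthesia monitor will be started"; the stimulus follows 60 seconds later. The Background describes the response as "an initial parasympathetic response rapidly followed by sympathetically mediated tachycardia and hypertension" and calls the changes brief.

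The Analytical Plan is a "paired T Test for continuous variables", with no reference to reading time. Methods and Measures plans 200 evaluable treatments from about 100 subjects, two each.

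**The concern.** The timer fixes the interval from study drug to stimulus. It does not fix when the cuff inflates. No section says that the pressure cycle is started or reset by the timer or the stimulus, or that the time of the reading is recorded.

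The response goes quickly from a parasympathetic to a hypertensive phase, so the value obtained depends on when it is taken. Two things follow if the cuff is not synchronised:

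- The two sessions of a pair are read at different points of the curve. That variation goes straight into the paired difference, and pairing does not remove it.
- Some readings may fall before the pressor phase that alfentanil is meant to blunt, which shrinks the average effect.

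Order is randomised and the anesthesia and data-collection staff are blinded, so neither problem favours an arm. What is at stake is a real effect being understated or missed on the only primary outcome.

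**Working it through.** **The plan's own figure.** 100 subjects × 2 treatments = 200 treatments, which agrees. It cannot be checked as a power calculation, because no alpha, power, effect size or SD is given.

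**Timing mismatch.** Assume each session's lag from stimulus to first reading is independent and uniform on 0–60 s.

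- Mean absolute difference between sessions: 60/3 = 20 s.
- SD of the difference: 60/√6 = 24.5 s.
- Probability of a difference over 30 s: (30/60)² = 0.25.

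**Effect on the paired t test.** All of the following are assumptions: 100 pairs, two-sided 0.05, peak rise R = 30, 40 or 50 mmHg on placebo, 30% lower on alfentanil, and other paired SD 20 mmHg. With f(t) the fraction of the peak reached at t seconds:

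paired difference = R·f(t₁) − 0.7R·f(t₂) + N(0, 20²)

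SD added by random timing = R·SD(f)·√(1 + 0.7²) = R·SD(f)·√1.49

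- Linear rise over 60 s: SD(f) = 0.289, so the added SD is 10.6/14.1/17.6 mmHg. For R = 40, the total SD is √(20² + 14.1²) = 24.5 mmHg.
- Rise to a plateau at 30 s: SD(f) = 0.323, so the added SD is 11.8/15.8/19.7 mmHg.

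The mean effect is 0.3·R·mean(f). This is 4.5/6.0/7.5 mmHg on the linear rise (mean f = 0.5) and 6.8/9.0/11.3 mmHg with the 30 s plateau (mean f = 0.75), against 9/12/15 mmHg at the peak.

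Power for R = 30/40/50 mmHg (random timing from 20,000 simulated trials per entry, fixed times from the noncentral t):

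| Response curve | Random timing | Same mean effect, no mismatch |
|---|---|---|
| Linear rise over 60 s | 0.50/0.68/0.80 | 0.61/0.84/0.96 (fixed 30 s) |
| Plateau at 30 s | 0.82/0.94/0.98 | 0.91/0.99/>0.99 (one shared random time per pair) |
| Plateau at 20 s | 0.91/0.98/>0.99 | – |
| No rise for 15 s, then a 30 s rise | 0.43/0.56/0.64 | – |

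The comparators differ because each keeps the mean effect as it is under random timing. On the linear rise, f(30) = 0.5 equals mean f; with the 30 s plateau a fixed 30 s reading would already be at the peak. Mismatch alone therefore costs about 0.11/0.16/0.16 on the linear rise and about 0.09/0.05/0.02 with the 30 s plateau. A fixed reading at the peak gives 0.99 or more on every curve, but part of that gain comes from choosing a better time, not from removing mismatch.

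**Sensitivity to the SD** (linear rise, R = 40; random against fixed 30 s): 0.82 against 0.98 at SD 15, and 0.43 against 0.51 at SD 30.

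**A second route.** Ignore the treatment effect on the slope and take a linear change over 60 s in both sessions. The added SD is (change/60) × 24.5, that is 4.1, 8.2 or 16.3 mmHg for changes of 10, 20 or 40 mmHg. With SD 20, 100 pairs are worth 100 × 20²/(20² + added SD²), which is about 96, 86 or 60 pairs.

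**The case against.** The strongest reply is that the loss depends on a practice the documents do not show. They say "A copy of the anesthetic protocol is posted for the providers reference at the point of care", and that sheet could hold a cuff-start instruction. The stimulus comes one full pressure cycle after the timer starts, so a cycle started with the timer would align with it. That is possible, and a synchronised cuff loses nothing. But the definition of a primary outcome should not rest on unwritten practice.

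The size is also open to challenge. The largest losses come from slow curves, while the Background speaks of a rapid change. With a plateau at 10 s, random timing gives 0.96/>0.99/>0.99, and mismatch costs 0.02 or less. Fully independent, uniform timing is close to a worst case. If the assumed 20 mmHg SD came from data gathered under routine 1-minute cycling, it would already contain some timing scatter. All of this stands: the loss runs from negligible to large, and the documents cannot say where this trial falls.

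Fixing the time also carries a risk. On the linear rise a fixed 15 s reading gives 0.20/0.32/0.46, worse than random timing, and the documents give no time course in seconds from which to choose. This stands as a condition on the fix.

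Finally, taking the first reading is a unique, prespecified rule applied alike in both arms. That is true, and it is why the concern is precision and not validity.

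**Conclusion.** The concern holds. Nothing in the document ties the reading that defines the primary outcome to a time after the stimulus, and the diastolic outcome has the same gap.

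There is no bias under the null. If the cuff is not synchronised, mismatch alone costs between about 0.02 and 0.16 of power across the linear and 30 s plateau curves at SD 20, and less with a faster plateau. Readings taken before the pressor phase also reduce the mean effect, to half its peak value on the linear rise. These sizes rest on assumed curves, rise, 30% reduction, SD and alpha, and on independent uniform timing; none of these is given in the documents.

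The change should be made: it costs little, and a reading taken at the wrong time cannot be recovered in the analysis.

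**What to change.** Define the primary and diastolic readings as cuff measurements started at one prespecified time, X s after the stimulus, the same in both sessions. Justify X as falling in the expected hypertensive phase and not in the early parasympathetic phase.

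The existing timer can deliver this. The stimulus is at 60 s and the cycle is 60 s, so a reading started when the timer shows X s puts the next one at X + 60 s, which is X s after the stimulus. No interval exceeds 1 minute, provided the manual start also restarts the automatic cycle; the site should confirm that on its monitor.

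Record the actual stimulus and cuff-start times in REDCap. Keep the paired t test as the primary analysis, and add a prespecified sensitivity analysis limited to pairs read within a stated window of the scheduled time. If the site already synchronises the cuff, say so in the protocol.

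The cost is one line in the posted anesthetic protocol, a few time fields, one sensitivity analysis and one manual cuff start per session. Treatment does not change, and no extra visits or staff are needed. The main risk is an X set too early, which is why it needs a written justification.

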### **HOLDING ROOM**

Glycopyrrolate 0.1 mg IV in the holding room.

Establish monitoring with baseline heart rate, blood pressures, manually recording each every 1 minute.

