### **PRIOR TO INDUCTION**

Recording 3 minutes of blood pressures, pulse oximetry and electrocardiogram, every 1 minute monitoring

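### Baseline heart rate is recorded before study drug but has no stated role as a covariate, and the plan does not say whether the 15 s and 30 s heart rates are raw values or changes from baseline.

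*Combined protocol and SAP*

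**What the plan says.** Methods and Measures sets the design and size: "A prospective, randomized, double blind, placebo-controlled AB/BA crossover study is planned", and "We aim to have 200 evaluable treatments involving the consent of an estimated 100 subjects".

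Heart rate is available before study drug. Under Holding Room: "Establish monitoring with baseline heart rate, blood pressures, manually recording each every 1 minute". Under Prior to Induction: "Recording 3 minutes of blood pressures, pulse oximetry and electrocardiogram, every 1 minute monitoring". The second list does not name heart rate, but an electrocardiogram and oximetry can supply it. Only later, under Induction, do we read that "the study medication (alfentanil or placebo) IV will be administered". Any pre-induction reading in a session therefore precedes that session's study drug.

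In Outcome Measure(s), both blood pressure outcomes are explicitly measured from baseline. Heart rate is treated differently. The text reads "Secondary outcomes include the within-individual differences of heart rate at 15 and 30 seconds post stimulus", with no statement of what is subtracted from what. Maximum and minimum heart rate follow with no reference value.

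The Analytical Plan is a single sentence. It describes the first-line analysis of continuous variables as a "paired T Test for continuous variables", with a signed-rank test for ordinal ones. It names no covariate, baseline or period term.

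**The concern.** Pairing removes stable differences between patients. It does not remove differences between a patient's two treatment days. If a patient arrives with a faster resting rate on one day, and that carries through to the post-stimulus rate, the shift enters the paired difference as noise. A baseline recorded in the same session, before study drug, can remove part of that noise. The plan collects the value but gives it no stated role in any heart-rate analysis.

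The Background names tachycardia alongside hypertension as the response of interest, and the hypothesis is about hemodynamic stability. The four heart-rate outcomes carry much of that question. If the interval is wider than the data allow, a small blunting of tachycardia is easier to miss. There is also a definitional gap. Raw and change-score versions of the 15 s and 30 s outcomes can differ appreciably in precision, and if the choice is left open it could be made after the data are seen.

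**Working it through.** **The plan's own figure.** 100 subjects × 2 treatments = 200 treatments, which agrees with the text and leaves no allowance for dropout. No alpha, power, effect size, SD or correlation is stated, so no power figure can be reproduced.

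**Set-up.** For each patient let D be the alfentanil-minus-placebo difference in the heart-rate outcome, B the same difference in baseline heart rate, and ρ the correlation of D with B. From the documents, n = 100 pairs. Assumed for illustration: two-sided alpha 0.05, ρ from 0 to 0.7, and normality.

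**Formulas.**
- Raw paired t-test: Var(D)/n.
- Regression of D on B, estimate taken at B = 0: (1 − ρ²) × (n − 2)/(n − 3) × Var(D)/n. With n = 100 the factor is 98/97 = 1.0103, the price of estimating the slope.
- Paired t-test on change from baseline, if D and B have equal SDs: (2 − 2ρ) × Var(D)/n.

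Example at ρ = 0.5: (1 − 0.25) × 1.0103 = 0.758, equivalent to 100/0.758 = 132 pairs.

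| ρ | Adjusted ÷ raw variance | Worth in pairs | Adjusted power where raw has 80% (effect 0.283 SD of D) | Change score ÷ raw variance |
|---|---|---|---|---|
| 0 | 1.010 | 99 | 79.6% | 2.00 |
| 0.1 | 1.000 | 100 | 80.0% | 1.80 |
| 0.2 | 0.970 | 103 | 81.2% | 1.60 |
| 0.3 | 0.919 | 109 | 83.2% | 1.40 |
| 0.5 | 0.758 | 132 | 89.6% | 1.00 |
| 0.7 | 0.515 | 194 | 97.4% | 0.60 |

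Break-even with the raw test is ρ = √(1 − 97/98) = 0.10. A simulation of 20,000 trials at each of ρ = 0, 0.3, 0.5 and 0.7 gave adjusted-to-raw variance ratios of 1.010, 0.913, 0.747 and 0.514, in agreement with the formula.

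**If the 15 s and 30 s outcomes are already changes from baseline.** With equal SDs, adjusted over change-score variance is (1 − ρ²)/(2 − 2ρ) = (1 + ρ)/2, times 1.0103. That is about 0.66 at ρ = 0.3 and 0.76 at ρ = 0.5. In general a change score beats the raw value only when the slope of D on B exceeds 0.5. When the slope is near 1 it matches adjustment.

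**In beats per minute.** Assume within-patient session SDs of 8 bpm at baseline and 14 bpm after the stimulus. The raw SE is √(2 × 14²/100) = 1.98. The change-score SE is √(2 × (8² + 14² − 2ρ × 8 × 14)/100).

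| ρ | Raw SE | Change SE | Adjusted SE |
|---|---|---|---|
| 0 | 1.98 | 2.28 | 1.99 |
| 0.3 | 1.98 | 1.96 | 1.90 |
| 0.5 | 1.98 | 1.72 | 1.72 |
| 0.6 | 1.98 | 1.58 | 1.59 |

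Power by true difference, under the same SDs:
- 4 bpm: 52% raw; adjusted 55% at ρ = 0.3 and 63% at ρ = 0.5.
- 6 bpm: 85% raw; adjusted 88% at ρ = 0.3.
- 8 bpm: 98% raw; adjusted 99% at ρ = 0.3 and 99.6% at ρ = 0.5.

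**The case against.** A reader might infer that all four heart-rate outcomes are analysed without baseline. The documents do not establish that. One sentence before the heart-rate outcomes, the primary outcome uses the same within-individual wording for a change from baseline, so the 15 s and 30 s values may already have baseline subtracted. Against that, the sentence listing the heart-rate outcomes names baseline for diastolic pressure and omits it for heart rate. The text is ambiguous, and only maximum and minimum heart rate clearly lack a baseline.

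A reader might also infer that a known amount of precision is being discarded at no cost. That is not supported either. Induction drugs, study drug, a 60-second wait and the stimulus all come between baseline and outcome, and nothing in the documents shows that ρ reaches 0.5. It may also differ between outcomes, minimum heart rate especially. Below about 0.1 the gain is nil or slightly negative, and for large effects power is already high without adjustment.

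It is also fair to say that the unadjusted comparison is valid, that these are secondary outcomes with no power claim, and that the plan presents the paired test as an initial analysis, so adjustment is not excluded. The same efficiency argument would reach the blood pressure change scores too.

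All of this limits the size of the point but does not remove it. Adjustment is at least about as precise under either reading of the 15 s and 30 s outcomes, and an adjustment not prespecified would be post hoc.

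**Conclusion.** The point holds as one of precision and definition. Baseline heart rate is collected before study drug, no analysis is stated to use it as a covariate, and the 15 s and 30 s outcomes are not defined well enough to tell a raw value from a change. There is no implied bias in the treatment comparison, no effect on type I error and no effect on the primary outcome.

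With 100 pairs, adjustment changes the variance relative to the raw paired test by about +1% at ρ = 0, −8% at 0.3 and −24% at 0.5. Its worst loss against either alternative is about 1%: against the raw test when ρ is near zero, and against a change score when the slope is near 1. These figures rest on an assumed ρ, on all 100 pairs being evaluable, and on the second session's baseline being free of carry-over from the first. The practical benefit is mainly for small effects. It is worth doing because it costs so little.

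**What to change.** Make three additions to Outcome Measure(s) and the Analytical Plan.

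1. State that heart rate at 15 s and 30 s is analysed as the raw value in each session, like maximum and minimum heart rate.
2. Name one pre-drug baseline heart rate per session, for example the mean of the one-minute readings before induction. If that choice is made, add heart rate to the Prior to Induction recording list, since only the Holding Room section names it now.
3. For the four heart-rate outcomes, regress each patient's alfentanil-minus-placebo difference on the corresponding baseline difference, with centred sequence in the model. Report the intercept as the adjusted mean difference with its confidence interval. Leave the baseline difference uncentred: centring it on its sample mean returns the unadjusted estimate.

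Do not use plain subtraction of baseline as a substitute, because it loses precision against the raw value when the slope is below 0.5.

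Cost: a few sentences, no new measurements, one degree of freedom for baseline and one for sequence. With balanced sequences, adding sequence moves the slope-estimation factor only from 98/97 = 1.0103 to 97/96 = 1.0104, so the loss if ρ is below about 0.1 stays at roughly 1% of variance.

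### Total in-room time includes a stretch before the study drug that alfentanil cannot change, which costs precision (not validity) in that secondary comparison

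*Combined protocol and SAP*

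**What the plan says.** Outcome Measure(s) lists, among many secondary outcomes, "total in-room time, time to return of spontaneous ventilation after induction". The ventilation clock is therefore tied to induction. No start or stop event is given for in-room time; its plain meaning is room entry to room exit.

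The order of events is clear. Background describes "alfentanil given post-induction of general anesthesia but pre-treatment with ECT". The Induction section starts with "Standard induction for ECT with methohexitol 1 mg/kg and succinylcholine 1 mg/kg" and continues: "After establishment of an adequate mask airway, and confirmation of adequate impedance on the ECT machine, the study medication (alfentanil or placebo) IV will be" given. It then adds: "A timer on the anesthesia monitor will be started". The next step, under the heading "60 SECONDS AFTER STUDY DRUG ADMINISTRATION", is the ECT stimulus. No outcome is defined from the timer, and the length of the gap between induction and study drug is neither fixed nor stated.

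Methods and Measures describes a randomized, double-blind AB/BA crossover with 200 evaluable treatments from about 100 subjects. The Analytical Plan uses a paired t test for continuous variables.

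**The concern.** Set-up, induction, airway and impedance time is over before the study drug is injected. Patients, anesthesia staff and data collectors are blinded and the order is randomized, so this segment carries no treatment effect. It does vary from one visit to the next, and under a paired t test that variation enters the SD of the within-patient difference.

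In-room time is the only listed outcome that measures room occupancy. If alfentanil lengthens the stay, the extra variance makes that harder to detect, and a null result is less informative than the same data could have made it.

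**Working it through.** **Inputs from the documents.** 100 subjects with two treatments each: 100 × 2 = 200, which agrees with the stated target. The analysis is a paired t test. The plan gives no alpha, power, effect size or SD, so there is no sample-size calculation to reproduce.

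**Assumptions.** Two-sided alpha 0.05; normal approximation; 80% power as the reference for the time from study drug to room exit.

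**In-room time.** Write it as P + R, with P from room entry to study drug and R from study drug to room exit. The expected treatment difference in P is zero, so P + R and R estimate the same treatment effect. Let k be the SD of the paired difference in P divided by that in R. If the two are independent, the SD of the paired difference is multiplied by √(1 + k²).

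- Standardized difference giving 80% power on R: (1.960 + 0.842)/√100 = 0.280.
- Power on P + R: Φ(2.802/√(1 + k²) − 1.960).
- Pairs needed to restore 80%: 100(1 + k²), rounded up.

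| k | SD multiplier | Power | Pairs for 80% |
|---|---|---|---|
| 0.25 | 1.03 | 77.6% | 107 |
| 0.5 | 1.12 | 70.7% | 125 |
| 0.75 | 1.25 | 61.1% | 157 |
| 1 | 1.41 | 50.8% | 200 |

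If the two differences have correlation ρ, the variance factor becomes 1 + k² + 2ρk. It falls below 1 only when ρ < −k/2, that is, when long set-ups go with short post-drug times. Otherwise R is at least as precise.

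**Ventilation time.** Let G be the gap from induction to study drug, and let return of breathing, counted from induction, be T = bG + e. Here b is how far a longer gap delays return of breathing. Counted from study drug, the time is T − G = −(1 − b)G + e. With the SD of the paired difference in e set to 1 and that in G set to k:

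- induction clock: variance 1 + b²k²
- study-drug clock: variance 1 + (1 − b)²k²

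The study-drug clock is more precise only if b > 0.5. At k = 0.5:

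| b | Power, induction clock | Power, study-drug clock |
|---|---|---|
| 0 | 80.0% | 70.7% |
| 0.5 | 77.6% | 77.6% |
| 1 | 70.7% | 80.0% |

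The documents give no value for b. If the paired difference is regressed on the paired difference in G, the two clocks give the same treatment estimate, because only the slope changes (b against b − 1).

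**The case against.** The best defense is that total in-room time is a whole-visit operational measure, to which pre-drug time properly belongs, and that it is unbiased as written. That stands, and it is why the figure should still be reported. The anesthetic is also standardized, which should limit pre-drug variation. The pre-induction step, "Recording 3 minutes of blood pressures, pulse oximetry and electrocardiogram, every 1 minute monitoring", has a set length, so it mainly shifts the mean, and the text does not say that it takes place in the procedure room. The SD ratio is unknown, and at k = 0.25 the loss is only about 2 power points. Both outcomes are secondary, and the sample size is not tied to either. The timer has an evident purpose already, which is to time the stimulus. All of this limits the importance of the point. None of it removes the added variance from the in-room comparison.

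A reader might infer two stronger points that the documents do not support.

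- **That pre-drug time is pure error in the ventilation outcome too.** Methohexitol and succinylcholine are given at induction and also bear on return of breathing, so the induction clock is a defensible choice. Moving it could lose power, as the b = 0 row shows.
- **That the ventilation end point is left to discretion.** The words "until the patient is spontaneously ventilating adequately per anesthesia discretion" say how long monitoring continues. They do not define the outcome. Capnography is described as monitored, and nothing says that the trace is kept, so this passage gives no ground for a capnography-based end point.

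**Conclusion.** The point holds for total in-room time, as a loss of precision without bias. The size cannot be computed from the documents. With 100 pairs, two-sided alpha 0.05, an independent pre-drug segment and 80% reference power, it runs from about 2 points (k = 0.25) through 9 points (k = 0.5) to 29 points (k = 1). Nothing in the plan shows that k is as large as 1. For return of spontaneous ventilation, no fault in the choice of clock is shown. This is a cheap improvement to one secondary outcome. It does not affect the primary analysis or the sample size.

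**What to change.** - Define the start and stop events of in-room time, and record the clock time of study drug administration, which the existing timer already marks.
- Compare treatments on time from study drug to leaving the procedure room, and report total in-room time alongside it.
- Keep return of spontaneous ventilation timed from induction. Derive the induction-to-drug interval from the recorded times and, as a supplementary analysis, adjust the paired difference for the between-period difference in that interval (regress one on the other; the intercept is the adjusted treatment effect). The interval ends before the blinded drug is given, so the adjustment is safe.

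The cost is one extra recorded time per treatment, some added outcome and analysis wording, and a less familiar operational figure for the in-room comparison. Treatment, procedures and sample size do not change.
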